3.5.2. Adverse Event of Special Interest (AESI)

AESIs include events such as CNS (mood, speech, cognition) events. These events will be defined based on a list of MedDRA Preferred Terms (PTs) specified in the Safety Review Plan for lorlatinib. A final list will be provided to programming prior to database release.

3.5.3. Laboratory Data

Hematology, chemistry, and lipids results will be programmatically graded according to the NCI CTCAE version 4.03 for relevant parameters. A shift summary of baseline grade by maximum post-baseline grade will be presented. Parameters which cannot be graded will be summarized relative to the normal range (ie, normal range high or normal range low). Additional details are provided in Section 6.6.1.

3.5.4. Vital Signs

Vital signs data will be summarized using descriptive statistics (mean, standard deviation (Std Dev), median, quartiles, minimum, and maximum) of actual values and change from

baseline for each nominal visit over time (ie, unscheduled assessments will be excluded). Additional details are provided in Section 6.6.2.

3.5.5. ECG

Descriptive statistics (n, mean, median, Std Dev, minimum, and maximum) of corrected QT (QTc) and other ECG parameters will be used to summarize absolute values and changes from baseline on treatment. Categorical analysis will be conducted for the maximum change from baseline in QTc, PR, and QRS and the maximum post-baseline QTc interval. Additional details are provided in Section 6.6.3.

4. ANALYSIS SETS (POPULATIONS FOR ANALYSIS)

Data for all participants will be assessed to determine if participants meet the criteria for inclusion in each analysis population prior to releasing the database and classifications will be documented per standard operating procedures.

Only participants who signed informed consent will be included in the analysis sets below.

Population	Description
Enrolled	All participants who sign the informed consent document.
Safety	All participants who receive at least 1 dose of lorlatinib.

5. GENERAL METHODOLOGY AND CONVENTIONS

All analyses will be performed at study participant data set release at the end of study, defined as 1 year after the last participant first visit (LPFV) date in the study.

5.1. Hypotheses and Decision Rules

5.1.1. Hypotheses and Sample Size

The primary objective of the study is to evaluate the safety and tolerability of single-agent lorlatinib in participants with unresectable advanced and/or recurrent ALK-positive NSCLC with resistance or intolerance to at least 1 prior ALK inhibitor treatment. No formal statistical hypothesis testing is planned for the primary objective.

This study will enroll enough participants to ensure that 100 participants are treated with lorlatinib.

5.1.2. Decision Rules

There is no decision rule for the primary objective.

5.2. General Methods

5.2.1. Definition of Study Day

Start day of study treatment is the day of the first dose of study treatment.

The study day for assessments occurring on or after the first dose of study treatment (e.g., adverse event onset, tumor measurement) will be calculated as:

Study day = Date of the assessment/event - start date of study treatment + 1.

The study day for assessments occurring prior to the first dose of study treatment (e.g., baseline characteristics, medical history) will be negative and calculated as:

Study day = Date of the assessment/event –start date of study treatment.

The study day will be displayed in all relevant data listings.

5.2.2. Definition of Cycle and Cycle Day

Cycle start and end dates are derived per participant. Treatment will be dispensed at the beginning of every 28-day cycle.

- For Cycle X, the actual cycle start date for each participant is:
 - o the earliest start date of dosing (dose>0 at that visit) in Cycle X visit Case Report Form (CRF) exposure page
- For all but the last cycle,
 - o actual cycle stop date is calculated as the start date of the next cycle minus one day.
 - o actual cycle duration is calculated from Day 1 of a cycle to the day prior to Day 1 of the next cycle, as follows:

Actual Cycle Duration (weeks) = (cycle stop date - cycle start date + 1) / 7

- For the last cycle, actual cycle duration is calculated as follows:
 - O Actual Cycle Duration (weeks) = (last date of study treatment–cycle start date + 1)/7

The cycle day will be calculated as:

Cycle day = Date of the assessment/event – cycle start date + 1.

5.2.3. Definition of Start of New Anticancer therapy

Start date of new anticancer therapy (drug, radiation, surgery) is used for definition of ontreatment in safety analyses (see Section 3.5.1) and for censoring in antitumor activity analyses (see Section 6.2.3).

The start date of new anticancer therapy is the earliest date after first dose of Lorlatinib amongst the following:

• Start date of anticancer drug therapy recorded in the 'Concomitant Medications' CRF pages with 'Category of medication' = 'Follow-up Cancer Therapy'

- Start date of radiation therapy recorded in 'Radiation Treatment' CRF page with 'Subcategory' = 'Curative in intent'
- Surgery date recorded in 'Non-drug Treatments' CRF pages with 'Category' = 'Cancer Surgery' and 'Outcome of Procedure' = 'Resected' or 'Partially Resected'.

When start date of anticancer therapy is missing or partially missing, the imputation rules described in Section 5.3.2.4 should be applied using 'Concomitant Medications', 'Radiation Treatment', and 'Non-drug Treatments' CRF pages.

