#### **Radiotherapy**

• Palliative radiotherapy on study is permitted for the treatment of painful bony lesions providing the lesions were known at the time of study entry and the Investigator clearly indicates that the need for palliative radiotherapy is not indicative of disease progression. In view of the current lack of data about the interaction of lorlatinib with radiotherapy, lorlatinib treatment should be interrupted during palliative radiotherapy, stopping 1 day before and resuming treatment after recovery from acute radiation toxicities to baseline.

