#### Bone lesions

- Bone scan, positron emission tomography (PET) scan or plain films are not considered adequate imaging techniques to measure bone lesions. However, these techniques can be used to confirm the presence or disappearance of bone lesions.
- Lytic bone lesions or mixed lytic-blastic lesions, with identifiable soft tissue components, that can be evaluated by cross sectional imaging techniques such as CT or MRI, can be considered as measurable lesions if the soft tissue component meets the definition of measurability described above.

• Blastic bone lesions are non-measurable.

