6.2. Secondary Endpoints

6.2.1. Confirmed OR

Analysis set: Safety: All enrolled participants who take at least 1 dose of Lorlatinib **Analysis methodology**:

• Objective Response Rate (ORR) defined as the percentage of participants with a confirmed best overall response (BOR) of CR or PR according to RECIST v1.1. BOR will be determined based on reported overall responses at different evaluation timepoints by the investigator from the date of treatment start until documented

disease progression or start of new anticancer therapy, according to the following rules:

- CR = at least two determinations of CR at least 4 weeks apart and documented before progression and start of new anticancer therapy
- PR = at least two determinations of PR or better (and not qualifying for a CR) at least 4 weeks apart and before progression and start of new anticancer
- o SD (for participants with at least one measurable lesion at baseline) = at least one SD assessment (or better and not qualifying for CR or PR) ≥ 6 weeks after date of treatment start and before progression and the start of new anticancer therapy
- Non-CR/Non-PD (for participants with only non-target disease at baseline) = at least one Non-CR/Non-PD assessment (or better and not qualifying for CR ≥ 6 weeks after date of treatment start and before progression and the start of new anticancer therapy
- o PD = progression ≤ 13 weeks after date of treatment start and not qualifying for CR, PR or SD
- O Not Evaluable (NE) = all other cases.

Clinical deterioration will not be considered as documented disease progression.

- participants without documented CR or PR will be considered as non-responders
- 95% CI interval for ORR using the Wilson's Score method

Intercurrent events and missing data:

- data on response after subsequent anticancer therapy is administered will be excluded
- participants with death prior to first post-baseline assessment, inadequate baseline
 assessment, new anticancer therapy started prior to first post-baseline assessment, and
 all post-baseline disease assessments missing will also be considered as nonresponders.

Summaries used for reporting:

- The frequency (number and percentage) of participants with BOR of CR, PR, SD, PD, non-CR/non-PD (applicable only to participants with non-measurable disease at baseline), and NE (not evaluable)
- ORR estimated by dividing the number of participants with OR (CR or PR) by the number of participants in the safety set

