6.2.2. Confirmed IC-OR

Analysis set: Participants with CNS metastases based on Investigator Assessment

Analysis methodology:

The IC-OR will be summarized similar to OR (as described above in section 6.2.1), in Safety Population with CNS metastases based on investigator assessment. Surgery or radiotherapy of extracranial lesions will not affect the determination of IC-OR.

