6.2.3. DoR

Analysis set: Subset of Participants with confirmed objective response

Analysis methodology:

DoR will be calculated on every participant showing OR as follows:

DoR (months) = [first date of PD or death/censoring – first date of CR/PR subsequently confirmed+1]/30.4375

DoR data will be censored as follows:

- For participants who start a new anticancer therapy prior to an event, censoring will be at the last adequate tumor assessment (see Section 5.2.9) prior to the start of new anticancer therapy. Note: if date of progression occurs on the same date as the start of new anticancer therapy, the progression will be counted as an event.
- For participants with documented progression or death after two or more missing tumor assessments, censoring will occur at the last adequate tumor assessment prior to the missing assessments. In this study antitumor activity will be assessed through radiological tumor assessments conducted at screening and every 12 weeks until disease progression regardless of initiation of subsequent anticancer therapy. The allowable time window for disease assessments is ±1week while on treatment and whenever disease progression is suspected (eg, symptomatic deterioration). Therefore time without adequate assessment is defined as 24 weeks plus 2 weeks.
- All other participants alive without objective progression will be censored on the date of the last adequate tumor assessment.

The date of tumor response at each nominal timepoint based on the investigator assessments will be used for determining the dates of last adequate assessment for censoring purposes.

The censoring and event date options to be considered for the DoR analysis are presented in Table 2.

Table 2. Outcome and event dates for DoR analyses

Scenario	Date of event/censoring	Outcome
Progression or death ≤ 26	Date of progression or death	Event
weeks after last adequate		
tumor assessment		
Progression or death > 26	Date of last adequate	Censored
weeks after the last adequate	assessment documenting no	
tumor assessment	PD prior to anticancer	
No progression	therapy or missed	
New anticancer therapy	assessments	
given prior to PD		

Intercurrent events and missing data: data on response after subsequent anticancer therapy is administered will be excluded.

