6.2.4. IC-DoR

Analysis set: Subset of Safety Participants with confirmed Intracranial objective response

Analysis methodology: IC-DoR (months) = [first date of PD in brain lesions or death/censoring – first date of IC-OR (CR/PR subsequently confirmed)+1]/30.4375

For participants whose IC-OR proceeds from PR to CR, the onset of PR is taken as the onset of response.

Censoring for IC-DoR will be identical to the censoring rules presented above for DoR.

Intercurrent events and missing data: data on response after subsequent anticancer therapy is administered will be excluded.

Summaries used for reporting: The IC-DoR will be summarized similar to DoR (as described above in section 6.2.3), in Participants with CNS metastases. Surgery or radiotherapy of extracranial lesions will not affect the determination of IC-DoR.

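### Palliative radiotherapy neither closes the response window nor censors duration, so the plan does not stop shrinkage of an irradiated target bone lesion from counting as response to lorlatinib

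*SAP*

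**What the plan says.** **Which radiotherapy counts.** SAP 5.2.3 defines the start of new anticancer therapy by drug, radiation or surgery. The radiation entry reads "Start date of radiation therapy recorded in 'Radiation Treatment' CRF page with 'Subcategory' = 'Curative in intent". SAP 6.5.5 repeats the restriction. Section 5.2.3 says its date serves both the on-treatment period of SAP 3.5.1 and the censoring in SAP 6.2.3. Section 3.5.1, however, ends the on-treatment period at follow-up radiation to a target or non-target lesion and says nothing about intent.

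**Where the date is used.** For best overall response, SAP 6.2.1 requires: "CR = at least two determinations of CR at least 4 weeks apart and documented before progression and start of new anticancer therapy". PR has a parallel rule. For DoR, SAP 6.2.3 states: "For participants who start a new anticancer therapy prior to an event, censoring will be at the last adequate tumor assessment". SAP 6.2.4 adds: "Censoring for IC-DoR will be identical to the censoring rules presented above for DoR". IC-OR follows the OR method, with the remark in SAP 6.2.2 that "Surgery or radiotherapy of extracranial lesions will not affect the determination of IC-OR".

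**Which radiotherapy is foreseen.** Protocol 5.6.2 (Radiotherapy) says: "Palliative radiotherapy on study is permitted for the treatment of painful bony lesions providing the lesions were known at the time of study entry". The investigator must state that it does not indicate progression, and lorlatinib is interrupted around it. Protocol Appendix 3 says that lytic or mixed bone lesions with a soft-tissue part assessable on CT or MRI "can be considered as measurable lesions if the soft tissue component meets the definition of measurability described above".

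**What is absent.** Appendix 3 asks whether a lesion in a previously irradiated area is measurable. Neither document says how to score a target lesion irradiated after baseline.

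**The concern.** The secondary estimand is described as the treatment effect of lorlatinib, and there is no control arm. Every measured shrinkage before progression or new therapy is therefore read as drug effect. Participants have unresectable advanced and/or recurrent disease, so radiotherapy during the study will mostly be palliative and the curative-intent trigger will seldom apply.

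The protocol foresees palliative radiotherapy to lesions that were present at baseline and may have been chosen as targets. Such a lesion can shrink from radiation while lorlatinib is interrupted, and SAP 2.1.2 does not treat interruption as an intercurrent event. If the shrinkage is reported as PR and confirmed, ORR rises. If the participant has already responded, local control by radiation can delay progression and lengthen DoR without censoring. Both errors favour the drug and could not be separated from drug effect afterwards.

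**Working it through.** **1. The plan's own figure.** The only design figure is the maximum standard error of an AE rate: sqrt(0.5 × 0.5 / 100) = 0.05, as stated in Protocol 9.2. This point does not depend on it.

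**2. Tracing the rule.** Take radiotherapy coded palliative to a target bone lesion.
- SAP 5.2.3: it sets no new-therapy date.
- SAP 6.2.1: the response window stays open.
- SAP 6.2.3: DoR is not censored.
- SAP 5.2.9: an assessment is adequate if the investigator gives a response category.
- Protocol Appendix 3, Table 5: a not-evaluable result exists when not all targets are evaluated, but no text directs its use for an irradiated target.

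Under SAP 3.5.1 the same radiotherapy, if regarded as follow-up radiation, would end the on-treatment period. Under 5.2.3 it would not. One date cannot satisfy both.

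**3. When one irradiated lesion can produce a PR.** Appendix 3 requires a fall of at least 30% in the sum of target diameters. Let w be the irradiated lesion's share of the baseline sum and s its proportional shrinkage, with all other targets unchanged. The condition is w × s ≥ 0.30, so s ≥ 0.30 / w.

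| Share w | Shrinkage needed |
|---|---|
| 100% (sole target) | 30% |
| 75% | 40% |
| 50% | 60% |
| 40% | 75% |
| 30% | 100% |
| below 30% | not possible alone |

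Example with assumed sizes: bone soft tissue 40 mm and lung 40 mm, sum 80 mm. The bone lesion falls to 15 mm (25/40 = 62.5%, above the 60% needed) and the lung lesion is unchanged. The sum is 55 mm and (80 − 55)/80 = 31.3%, a PR if confirmed at least 4 weeks later.

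**4. Effect on ORR.** The denominator is the safety set, n=100, so each case is 1/100 = 1 point. The documents give no frequency, so k, the number of responders who would be reclassified, is assumed. The starting value of 32 responders is also assumed, taken from the 9/28 = 32% in the protocol background. Intervals are 95% Wilson score, the SAP's method.

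| k | ORR | 95% CI |
|---|---|---|
| 0 | 32% | 23.7–41.7 |
| 1 | 31% | 22.8–40.6 |
| 3 | 29% | 21.0–38.5 |
| 5 | 27% | 19.3–36.4 |

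**5. Effect on IC-ORR, if it arises.** The number with CNS metastases is not given. Assuming 30 to 60, one case is 1/30 = 3.3 to 1/60 = 1.7 points. At an assumed 40 participants and 22 responders, one case moves 55.0% (39.8–69.3) to 52.5% (37.5–67.1).

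**The case against.** **The investigator decides.** Best overall response is built from the investigator's reported responses, and nothing forces an irradiated lesion to be scored as PR. A reader might infer that the plan credits radiation shrinkage to lorlatinib. The documents support only that nothing prevents it. The gap remains, because sites may differ and no rule guides them.

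**The restriction looks deliberate.** It appears in both 5.2.3 and 6.5.5, and it fits a protocol that treats permitted palliative radiotherapy as not indicating progression. That is a good reason to leave radiotherapy to non-target bone lesions neutral. It does not settle how to measure a target that has been irradiated.

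**The intracranial case is weak.** A reader might infer that all four response endpoints are equally exposed, or that the remark on extracranial lesions in SAP 6.2.2 and 6.2.4 shows that all intracranial local therapy was meant to count. Neither follows. The remark makes full sense as an exception to 5.2.3, under which intracranial resection and curative-intent radiotherapy already count. The protocol does not list brain radiotherapy as permitted during the study. After documented intracranial progression the IC-OR window is closed and the IC-DoR event has occurred. What is left is palliative-coded brain radiotherapy before documented progression, followed by a scan. Protocol 7.1 schedules scans only to the end of treatment, although SAP 6.2.3 describes them as continuing to progression.

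**The effect is small.** These are secondary, descriptive endpoints, and 1 point is little against a Wilson interval of about 18 points. This stands, and it limits the priority of the point.

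**Conclusion.** The gap is real for ORR and DoR through irradiated target bone lesions, and secondary for IC-OR and IC-DoR. The conflict between SAP 3.5.1 and 5.2.3 is a separate, plain inconsistency.

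Each affected participant is worth 1 point of ORR at n=100. The total bias cannot be derived, because the documents do not give the frequency of palliative radiotherapy to target lesions. It arises mainly where there are few targets and the irradiated lesion dominates the sum. The effect on DoR cannot be sized either; its direction is toward longer duration when radiation delays growth of the irradiated lesion. The conclusion assumes that investigators report the measured response without declaring the lesion not evaluable. The AE incidence endpoint is touched only through the 3.5.1 wording. This is a change that should be made because it is cheap and removes a bias favouring the drug. It does not threaten the trial's main purpose.

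**What to change.** 1. **Reconcile SAP 3.5.1 with 5.2.3** so that one stated definition of radiotherapy governs the on-treatment period. Keep the response rule below in SAP 6.2, so that it does not alter the AE window.
2. **SAP 6.2.1 and 6.2.3:** state that a target lesion irradiated after the first dose, whatever the coded intent, is not evaluable for response from that date, while growth or new lesions still count as PD. State that palliative radiotherapy to non-target bone lesions stays neutral. Because SAP 5.2.9 does not treat a not-evaluable time point as adequate, say also whether the 26-week rule in SAP Table 2 applies when scans were done but scored not evaluable only for this reason.
3. **IC-OR (SAP 6.2.2):** do not credit a response first documented after radiotherapy to an intracranial lesion, whatever the intent.
4. **IC-DoR (SAP 6.2.4):** keep the current rule and report censoring at such radiotherapy as a sensitivity analysis. Making it the main rule could bias the other way: if radiotherapy is prompted by worsening not yet documented as PD, the censoring is informative and can drop a later event.

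Surgery needs no addition, since resection and partial resection already count under 5.2.3. No change to when radiotherapy may be given is proposed.

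**Cost:** a short SAP addition, programming, and a brief instruction to sites, because responses are investigator-reported. The irradiated site must be available from the existing Radiation Treatment CRF page, which cannot be checked from these documents. Expect slightly fewer responders.

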5.2.4. Date of Last Contact

The date of last contact will be derived for participants not known to have died at end of the study using the latest complete date (i.e. imputed dates will not be used in the derivation) among the following:

- All participant assessment dates e.g. tumor assessments,
- Start and stop dates of concomitant therapies including non-drug treatments or procedures,
- Start and end dates of anticancer therapies administered after study treatment discontinuation including systemic therapy, radiation, and surgeries,
- AE start and end dates,
- Date of first and last dose,
- Vital sign, ECG, laboratory and weight assessment dates
- Date of discontinuation on disposition CRF pages (do not use if reason for discontinuation is lost to follow-up or death).

Only dates associated with actual examinations of the participant will be used in the derivation.

5.2.5. Measurable Disease

A participant will be considered to have measurable disease if there is at least one target lesion identified at baseline meeting the following criteria:

- Non lymph node lesions with longest diameter ≥ 10 mm by Computerized Tomography (CT) scan,
- Non lymph node lesions with longest diameter ≥ 10 mm caliper measurement by clinical exam,
- CNS lesions with longest diameter ≥5 mm provided by gadolinium contrast enhanced Magnetic Resonance Imaging (MRI) performed with contingent slices of 1 mm, or

• Lymph nodes with short axis ≥ 15 mm when assessed by CT.

5.2.6. Tumor Assessment Date

The Date of Tumor Assessment at each nominal timepoint as provided by the investigator on the Investigator Overall Tumor Assessment (IOTA) CRF will be utilized for the respective analyses.

